5. Procedures for Minimizing Risks: We will do everything possible to minimize the risks associated with participating in the studies. We will ensure there are no contraindications to receiving rivaroxaban. This study will be monitored by a DSMB, which will review all reports to determine if there is a safety concern. Finally, we have established data safety and monitoring procedures as described below.

Risks to Privacy: All clinical information, including personal identifiers obtained on research subjects will be maintained in a locked and secured file drawer with access limited to clinical staff. All data will be coded to protect patient confidentiality. We will make all effort to maintain patient confidentiality.

6. Potential Benefits of the Proposed Research to the Subjects and others: The available treatments in SCD remain limited. This study will help to define the contribution of coagulation activation to the pathophysiology of SCD.

7. Importance of the Knowledge to be Gained: Despite our improving understanding of the pathophysiology of SCD, treatment options for several SCD-related complications remain quite limited. This proposal aims to increase our understanding of the contribution of coagulation

Rivaroxaban in Sickle Cell Disease

activation to the pathophysiology of SCD. The risks to patients from participating in this study are modest and are reasonable in relation to the potential benefits and the importance of knowledge to be gained.

8. Data and Safety Monitoring Plan: All SAEs will be reported to the IRB and the DSMB. In addition, after 5 patients and subsequently every 6 months, all of the available safety data will be presented by treatment group to the DSMB in a confidential report. The DSMB will review and determine if there is a safety concern. The DSMB will review the study after the occurrence of the first treatment-associated SAE. The study will be terminated at the occurrence of 3 treatment-related serious adverse events, including bleeding complications. The statistician who conducts the randomization and generates the tables for the DSMB will be an 'independent statistician' not otherwise involved in the study and will not be responsible for the data analysis at the completion of the study.

The UNC TraCS DSMB is a committee that has been established within the UNC School of Medicine. The membership is appointed by the Dean (or his designee), and is available to review any clinical trial that is being carried out by a UNC investigator. Most multi-center clinical trials funded by the NIH or by industry have national data and safety monitoring boards organized by the sponsoring organization. However, single- or dual-site clinical trials such as the study proposed in this application depend on a local DSMB such as the one based here at UNC. The current makeup includes a chair ([name]), an ethicist, an epidemiologist/biostatistician, and several clinical researchers. In addition, *ad hoc* members are added to the DSMB when need for scientific expertise arises.

9. Inclusion of Women and Minorities: Based on the results of our studies in this patient population to date, we anticipate that enrolled subjects will include 50-55% women. We have achieved this in the past without special efforts to recruit women, and this reflects the gender distribution of our patient population. In addition, due to the nature of the disease to be studied (sickle cell disease), over 95% of patients will identify themselves as African-American. A small number identifying themselves as Hispanic or Native American may be available; such patients typically comprise less than 2% of our clinic patients with this disease.

10. Inclusion of Children: As rivaroxaban is not yet approved in children, no patients less than 18 years will be evaluated in this study.

	Screening ¹	Treatment 1		2 Week Treatment 2 Washout			2	F/U	
Assessment/Event	Day -281	BL^1	Wk 2	Wk 4		BL	Wk 2	Wk 4	Wk 6
Informed consent	Х								
Medical history	Х			_					
Vital Signs	Х	Х	Х	X		Х	Х	Х	Х
Physical exam	Х	Х		_		Х			Х
MRI/MRA	Х								
Hematology ²	X	Х				Х			Х
Chemistries ³	Х	Х				Х			X
Coags ⁴	Х	Х				X			X
Chest X-ray	Х								
Serum/urine pregnancy test ⁵		Х	Х	X		Х	X	X	
Biomarkers		Х	Х	X		X	Х	Х	
Laser doppler velocitometry		Х		X		X		Х	
Randomization		Х							
Study drug initiation		Х				Х			
Adverse event probe		Х	Х	X		Х	Х	Х	Х
Record concomitant medications	Х	Х				Х			Х

¹ Screening assessments and baseline assessments for Treatment Phase 1 may be combined if eligibility can be established before treatment is initiated ² CBC with differential and reticulocyte count ³ BUN, creatinine, albumin, total and direct bilirubin, ALT, AST, LD, AlkPhos, GGT ⁴ PT/INR and aPTT

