Hypothesis: Inhibition of FXa will reduce coagulation, inflammation, and endothelial cell activation and improve microvascular blood flow in patients with SCD. We will perform a proof-of-concept study using the FXa inhibitor, rivaxoxaban, to: (i) evaluate the effects of rivaroxaban on coagulation, inflammation and markers of EC activation in SCD patients during the non-crisis, steady state; (ii) determine the effects of rivaroxaban on microvascular blood flow in SCD patients during the non-crisis, steady state; and (iii) assess the safety of rivaroxaban in patients with SCD.

Rivaxoxaban

Rivaroxaban is an oral direct factor Xa inhibitor that selectively blocks the active site of factor Xa. In addition, it inhibits prothrombinase activity, clot-associated factor Xa, and thrombin generation. This mechanism is unique to small, direct inhibitors because factor Xa that is incorporated in the prothrombinase complex is protected from inhibition by antithrombin and by antithrombin-dependent anticoagulants. Rivaroxaban is metabolized in the liver through oxidative and hydrolytic processes catalyzed by cytochrome P450 (CYP) 3A4/5 and 2J2. It is also a substrate for the P-glycoprotein efflux transporter protein. Approximately 66% of rivaroxaban is excreted in the kidneys (36% as unchanged drug), and the remainder is excreted in the feces as unchanged drug. In healthy, white men between 19 and 45 years, the administration of a single dose of rivaroxaban (5 to 80 mg) resulted in a maximum factor Xa inhibition of 20% to 80% within 1 to 4 hours after administration. After administration of the drug, maximum concentration was attained in 2 hours and the half-life was between 6 and 7 hours. Rivaroxaban prolonged the prothrombin time, activated partial thromboplastin time, and HepTest (a lowmolecular-weight heparin [LMWH] activity assay), but had no effect on thrombin or antithrombin activity. In a study with multiple doses of rivaroxaban (5 mg once or twice daily to 30 mg twice daily) administered to healthy men aged 20 to 45 years, the maximum concentration was reached in 2 to 4 hours and maximum factor Xa inhibition ranged from 22% (5-mg dose) to 68% (30-mg dose). Based on data from a multiple-dose study, rivaroxaban has predictable, doseproportional pharmacokinetic and pharmacodynamic properties. The AUC of rivaroxaban is increased by 50% and the half-life prolonged to between 11 and 13 hours in elderly patients compared with younger patients.

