Moderate renal impairment (creatinine clearance [CrCl] of 30–49 mL/min) and increased age lead to slight increases in rivaroxaban exposure. A rivaroxaban dose of 15 mg daily in patients with CrCl of 30 to 49 mL/min achieves a maximum concentration similar to that observed with a dose of 20 mg daily in patients with normal renal function. The increases in the AUC of inhibition of factor Xa activity are 50%, 86%, and 100% for mild, moderate, and severe renal impairment, respectively. In patients being treated for nonvalvular atrial fibrillation, it is recommended to reduce the dose of rivaroxaban to 15 mg once daily if the CrCl is 15 to 50 mL/min. It is recommended that the use of rivaroxaban be avoided in patients with moderate (Child-Pugh B) and severe (Child-Pugh C) hepatic impairment or with any hepatic disease associated with a coagulopathy. Drugs that are combined p-glycoprotein and CYP3A4 inhibitors, including "azole" antifungals and HIV protease inhibitors, result in increases in rivaroxaban exposure and factor Xa inhibition. Drugs that are combined p-glycoprotein inducers and strong CYP3A4 inducers such as rifampicin (which cause 50% and 22% decreases in AUC and maximum concentration, respectively), phenytoin, carbamazepine, and St. John's wort

Rivaroxaban in Sickle Cell Disease

should also be avoided with rivaroxaban administration. The pharmacokinetic and pharmacodynamic properties of rivaroxaban are not affected by the co-administration of aspirin, naproxen, ranitidine, omeprazole, or aluminum-magnesium hydroxide. Rivaroxaban exposure is reported to be lower after meals and the presence of food delayed the time to maximum concentration, but increased both the maximum plasma concentration and AUC at doses greater than 10 mg. It is recommended to take 15- and 20-mg tablets of rivaroxaban with the evening meal. The absolute bioavailability of the 10 mg rivaroxaban tablet is not affected by food and this dose can be taken either with or without food.

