We will conduct a randomized, double-blind, placebo-controlled, crossover study to evaluate the efficacy and safety of rivaroxaban in SCD. We have selected this agent based on our preliminary data in sickle mice showing that 'upstream' TF inhibition achieves the desired effects on inflammation and endothelial activation, but that 'downstream' thrombin inhibition does not. The study will consist of three phases: 1) Screening/Baseline; 2) Treatment; and 3) Follow-up. The Screening/Baseline Phase will occur within 28 days of study drug administration and will include: informed consent, a history and physical examination, and clinical laboratory tests including: a complete blood count, routine coagulation studies, routine chemistries, chest x-ray, and serum or urine pregnancy test (if female, and of child-bearing capacity). The sequence of drug administration will be generated via block permuted randomization procedure. The 4-week Treatment Phase will consist of drug administration, efficacy assessments and safety assessments (including pregnancy testing in females of child-bearing capacity). After the first treatment period, there will be a washout period of 14 ± 3 days. In the second treatment phase, patients will be crossed over to receive rivaroxaban or placebo, depending on their initial treatment assignment. The total duration of the Treatment phase (including washout) will be 10 weeks. During the Follow-up Phase at week 12, patients will obtain their final study evaluation. Table 2 provides a detailed schedule of assessments for the study period.

Treatment: Subjects will receive rivaroxaban 20 mg/day (the approved dose to prevent stroke and systemic embolism in patients with non-valvular atrial fibrilation) and placebo for 4 weeks each, separated by a 2-week washout phase. Pill counting will be used to assess compliance. PT/INR will be monitored by an unblinded investigator to assess compliance with no other involvement in the study). If major bleeding or other serious adverse event occurs (see Appendix 2), the study drug will be discontinued and the patient followed until resolution of the problem. Subjects that discontinue the study early will not be replaced.

Eligibility Criteria:

Inclusion Criteria:

- a) 18 to 65 years of age;
- b) HbSS or HbS β 0 thalassemia; serum creatinine $\leq 1.0 \text{ mg/dL}$ men) or 1.2 mg/dl (women);
- c) ALT ≤ 2 times upper limits of normal;
- d) platelet count \geq 150,000 cu/mm;

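### Renal eligibility uses a serum creatinine ceiling with no clearance floor, so some lighter women, especially older ones, could receive the fixed 20 mg dose with estimated clearance below 50 mL/min.

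*Combined protocol and SAP*

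**What the plan says.** Under Eligibility Criteria, inclusion (b) caps serum creatinine at 1.0 mg/dL for "men) or 1.2 mg/dl (women"). It gives no reason for the higher limit in women. No inclusion or exclusion criterion names a creatinine clearance or an eGFR.

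Under Research Design and Methods, Treatment, all subjects receive 20 mg/day for 4 weeks. The dose is described as "the approved dose to prevent stroke and systemic embolism in patients with non-valvular atrial fibrilation". No renal dose adjustment is stated.

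The background section on rivaroxaban reports the following:

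- In the atrial fibrillation setting, "it is recommended to reduce the dose of rivaroxaban to 15 mg once daily if the CrCl is 15 to 50 mL/min".
- On peak levels, "A rivaroxaban dose of 15 mg daily in patients with CrCl of 30 to 49 mL/min achieves a maximum concentration similar". The comparison is with 20 mg when renal function is normal.
- Older age and a clearance of 30–49 mL/min are each said to "lead to slight increases in rivaroxaban exposure".
- The AUC of factor Xa inhibition rises by "50%, 86%, and 100% for mild, moderate, and severe renal impairment" respectively.

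Under Human Subjects, Procedures for Minimizing Risks, the protocol adds a general assurance: "We will ensure there are no contraindications to receiving rivaroxaban". It names no renal value.

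**The concern.** The protocol adopts the atrial fibrillation dose without the renal condition that its own background attaches to that dose. Serum creatinine is a poor stand-in for clearance in small or older people: at the same creatinine, clearance falls with age and with body weight, and is lower in women. The higher limit applies to women, so the gap is widest where a given creatinine corresponds to the lowest clearance.

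At stake is bleeding safety. Some women could take full-dose anticoagulant for 4 weeks at a clearance where the source indication would use a lower dose. Safety is a stated aim, the protocol acknowledges that experience with rivaroxaban in sickle cell disease is very limited, and the study stops at three treatment-related serious adverse events. Efficacy is not affected: in a crossover each patient serves as her own control, so the comparison with placebo is not biased.

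**Working it through.** The plan gives no clearance figure, so there is none to reproduce. The check is whether a patient who meets inclusion (b) can have a clearance in the range where the background reports a dose reduction.

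**Inputs from the document.** Creatinine limits of 1.0 mg/dL (men) and 1.2 mg/dL (women); age 18 to 65; dose 20 mg/day; dose-reduction range 15 to 50 mL/min.

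**Assumptions.** Cockcroft-Gault for clearance, and body weights of 50 to 90 kg. The document supplies neither.

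**Formula.** CrCl = (140 − age) × weight / (72 × creatinine), multiplied by 0.85 for women.

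**Worked case.** Woman aged 65, 60 kg, creatinine 1.2: 75 × 60 × 0.85 / (72 × 1.2) = 3825 / 86.4 = 44.3 mL/min.

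**Women at 1.2 mg/dL (mL/min):**

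| Age | 50 kg | 60 kg | 70 kg | 80 kg | 90 kg |
|---|---|---|---|---|---|
| 65 | 36.9 | 44.3 | 51.6 | 59.0 | 66.4 |
| 60 | 39.4 | 47.2 | 55.1 | 63.0 | 70.8 |
| 50 | 44.3 | 53.1 | 62.0 | 70.8 | 79.7 |
| 40 | 49.2 | 59.0 | 68.9 | 78.7 | 88.5 |

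At age 30 every value is 54.1 or more.

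**Weight at which clearance equals 50.** Weight = 50 × 72 × creatinine / ((140 − age) × 0.85). For women at 1.2 the numerator is 4320:

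- age 40: 4320 / 85 = 50.8 kg
- age 50: 4320 / 76.5 = 56.5 kg
- age 60: 4320 / 68 = 63.5 kg
- age 65: 4320 / 63.75 = 67.8 kg

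**How near the ceiling she must be.** A 65-year-old woman reaches 50 mL/min at a creatinine of weight × 63.75 / 3600: 0.89 mg/dL at 50 kg, 1.06 at 60 kg and 1.24 at 70 kg.

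**Men at 1.0 mg/dL.** The lowest value for these weights is at age 65 and 50 kg: 75 × 50 / 72 = 52.1 mL/min. A man of 65 falls below 50 only under 3600 / 75 = 48.0 kg.

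**If the two limits were transposed.** At age 65, women at 1.0 would be below 50 under 3600 / 63.75 = 56.5 kg, and men at 1.2 under 4320 / 75 = 57.6 kg. The gap narrows for women, opens for some men and does not close.

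**Size of the pharmacological effect.** The background also says that "rivaroxaban has predictable, doseproportional pharmacokinetic and pharmacodynamic properties". If so, matching 15 mg at a clearance of 30–49 to 20 mg in normal function implies a peak concentration of about 20/15 = 1.33 times normal when 20 mg is given in that range. The reported AUC of factor Xa inhibition is 86% higher in moderate impairment.

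**The case against.** The strongest reply is that this is a corner case. Age alone is never enough: at 70 kg or more, no eligible woman falls below 50 mL/min. Over ages 65, 60, 50, 40 and 30 and the five weights, 6 of 25 combinations are below 50 at a creatinine of exactly 1.2 (one of them at 49.2), and at 1.0 only 2 of 25 remain. With 50–55% women expected among 34 patients, about 17 to 19 women would enrol, and possibly none would be affected. All of this stands, and it limits the size of the point.

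The result also depends on the formula. On CKD-EPI 2021, a woman at 1.2 mg/dL has an indexed eGFR of 50.2 mL/min/1.73 m² at age 65 and 55.1 at age 50, so no shortfall appears. That stands as a sensitivity result. However, the background states its threshold as creatinine clearance, and an indexed value ignores body size, which is the issue for small women.

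The clinical consequence may be modest. The background calls the exposure increase slight and presents the 15 mg rule as a recommendation in another disease. A floor at 50 would still admit mild impairment, reported at +50%, so comparing moderate with mild gives 1.86 / 1.50 = 1.24-fold. This is fair, but the dose was chosen by reference to that other indication.

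Other safeguards exist: normal baseline PT/INR and aPTT, platelets of at least 150,000, exclusions for bleeding history and interacting drugs, chemistries before each treatment period, discontinuation on the investigator's judgment, and DSMB review. None sets a renal threshold before dosing. PT/INR during treatment is monitored for compliance, and the schedule marks no chemistries at weeks 2 or 4. A general check for contraindications need not catch a clearance that the background treats only as a reason to lower the dose.

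**Conclusion.** The concern holds. Inclusion (b) admits women whose estimated clearance lies in the range where the protocol's own background reports a lower dose for the indication that supplied the 20 mg. For a woman at the creatinine limit, this happens below 67.8 kg at age 65, falling to 50.8 kg at age 40. The conclusion rests on Cockcroft-Gault and on assumed weights, and it concerns women near the ceiling. How many would be enrolled cannot be derived from the document. No endpoint, power figure or treatment comparison changes. It is a safety gap of limited reach that is cheap to close.

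**What to change.** Add to inclusion (b): *and estimated creatinine clearance above 50 mL/min (Cockcroft-Gault, from screening creatinine, age, sex and weight)*. Name weight in the screening column of the schedule; it may already be taken with vital signs or the physical examination, but it is not listed.

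While editing the criterion, confirm that the two sex-specific creatinine limits are the intended way round. The clearance floor is needed whatever the answer, because a swap leaves some women and some men below 50 mL/min at age 65.

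The cost is one clause and one schedule entry, since creatinine is already measured at screening. The downside is that a few lighter or older candidates would be excluded from a trial of about 34 patients.

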Study Design: This is a randomized, double-blind, placebo-controlled, crossover study of rivaroxaban to evaluate the efficacy and safety of rivaroxaban in SCD. It will be divided into a Screening/Baseline phase, Treatment phase, and Follow-up phase.

Study Population: Thirty two patients with SCD (HbSS or HbS β^0 thalassemia) between the ages of 18 and 65 who meet the eligibility criteria and provide consent to participate in the study, will be randomized in this crossover trial.

Clinical and Laboratory Evaluations: The Screening/Baseline Phase will occur within 28 days of study drug administration and will include: informed consent, a history and physical examination, and clinical laboratory tests including: a complete blood count, routine coagulation studies, routine chemistries to assess liver and renal function chest x-ray, brain MRI/MRA scan and serum or urine pregnancy test (if female, and of child-bearing capacity). During the Treatment Phase, we will also obtain a complete blood count, routine chemistries to assess liver and renal function, and pregnancy test (if female); and prior to the second treatment phase, a repeat history and examination and laboratory studies will be performed, which will serve as a baseline for the second treatment phase. Finally, measurements of microvascular blood flow (assessed non-invasively using laser Doppler velocimetry), endothelial activation (soluble VCAM, soluble ICAM), coagulation activation (TAT and D-dimer) and markers of inflammation (IL-6, high sensitivity CRP, MPO, IL-2, IL-8, TNF α , sPLA2) will be obtained at specified time points during the Baseline, Treatment and Washout/Follow-up Phases. The Follow-up Phase will consist of safety assessments performed four weeks after the final dose of study treatment.

Title of the Protocol: The effect of factor Xa inhibition, with rivaroxaban, on the pathology of sickle cell disease

Sample Size: In a 2x2 crossover design, assuming a correlation of 0.65 for the pre- and posttreatment measures, to detect a difference of 0.245 in the change of log(sVCAM) and 0.475 in the change of log(IL-6) between the rivaroxaban and placebo groups requires a minimum sample size of 15 per sequence (a total sample size of 30) at 80% power and α =0.05. Assuming a 10% dropout rate, a total of 34 patients is required for this study (17 in each sequence).

Randomization: 1:1 randomization to receive rivaroxaban or placebo.

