- e) normal baseline PT/INR and aPTT;
- f) be in the non-crisis, "steady state" at enrollment with no severe pain episodes during the preceding 4 weeks;
- g) ability to understand the requirements of the study and be willing to give informed consent;
- h) women of childbearing age must be practicing an adequate method of contraception;
- i) if on hydroxyurea, must be on a stable dose for at least 3 months. The dose of hydroxyurea will not be adjusted during the study duration except for safety reasons.

Exclusion Criteria:

- a) hypersensitivity to any component of rivaroxaban;
- b) history of major GI bleeding or bleeding diathesis;
- c) baseline Hb < 5.5 g/dL;
- d) history of clinically overt stroke;
- e) brain MRI/MRA scan with evidence of Moya Moya;
- f) pregnant or breastfeeding;
- g) active liver disease or ALT > 3 times upper limit of normal;
- h) on chronic anticoagulant, NSAID or statin therapy;
- i) history of metastatic cancer;
- j) current alcohol abuse;
- k) on a chronic transfusion program or any blood transfusion in the prior 3 months;
- 1) ingested any investigational drugs within the past 4 weeks
- m) use of CYP3A4/P-glycoprotein inducers such as carbamazepine, phenytoin, rifampin, and St John's wort;
- n) use of CYP3A4/P- glycoprotein inhibitors such as ketoconazole, indinavir/ritonavir, itraconazole, lopinavir/ritonavir, ritonavir, and conivaptan

Assessments: Activation of coagulation.: Plasma levels of TAT and D-dimer measured using a commercially available ELISA kit at baseline, and at 2 and 4 weeks following initiation of study drug

Endothelial cell activation: Plasma levels of soluble VCAM-1 and soluble ICAM-1 measured using a commercially available ELISA kit at baseline, and at 2 and 4 weeks following initiation of study drug

Inflammatory markers: Plasma levels of IL-6 (commercially available ELISA), high sensitivity CRP, MPO, IL-2, IL-8, TNFα, sPLA2 (multiple cytokine assay using Luminex MAP technology; UNC core facility) at baseline, and at 2 and 4 weeks following initiation of study drug

Microvascular blood flow: We will analyze microvascular blood flow using laser Doppler velocimetry (LDV) (Perimed, PF5001, Stockholm, Sweden) assessments of post-occlusive reactive hyperemia (PORH). Measurements will be obtained at baseline and at 4 weeks following initiation of therapy.

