Safety Assessment: We will evaluate patients for major bleeding complications (any bleeding episode into critical sites, e.g. intracranial bleed, decrease in hemoglobin concentration of at least 2g/dL from baseline or any prolonged bleeding that requires a blood transfusion) and other clinically relevant non-major or trivial bleeding. We will also evaluate for episodes of SCD-related events during scheduled follow-up visits, by employing a systems review, physical examination, vital signs, and routine laboratory tests.

Termination Criteria: Treatment with study drug will be discontinued at any time if the patient: a) withdraws consent; b) develops a major bleeding episode (defined as any bleeding episode into critical sites, e.g. intracranial bleed, decrease in hemoglobin concentration of at least 2g/dL from baseline or any prolonged bleeding that requires a blood transfusion); or if, c) in the judgment of the investigator, continuation of the study drug will be hazardous to the patient. The UNC DSMB will review the protocol following the occurrence of the 1st treatment-related serious adverse event. The study will be terminated at the occurrence of treatment-related serious adverse events, including major bleeding, in up to 3 study participants.

STATISTICAL METHODS

Normally distributed variables will be presented with means and SD, while summary of variables not normally distributed will be presented with medians and ranges or geometric means and SD as appropriate. The main study objective is to examine the difference between the measurements at baseline and following 4 weeks of treatment. We will evaluate the effect of rivaroxaban on the outcome measures by performing a comparison of treatment by visit using paired t-tests subsequently followed by crossover ANOVA model testing to assess the carry-over effect and treatment effect. In addition, when outcome measures are not normally distributed, we will perform appropriate nonparametric tests. The effect of rivaroxaban on various plasma markers and microvascular blood flow will be estimated using a multiple linear regression model. While the study is adequately powered to evaluate the effect of rivaroxaban on soluble VCAM-1 and IL-6, analysis of the effect of rivaroxaban on the other indicated endpoints are exploratory.

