2. Sources of Research Material: Enrollment and study participation will involve the collection of a full range of clinical data, including medical history. We will obtain clinical and laboratory data as well as assessments of microvascular blood flow at specified intervals during the course of the studies as described in the research plan.

3. Plans for Recruitment: Patients will be recruited from amongst the patients that routinely receive their care at the UNC Comprehensive Sickle Cell Program. [name] and/or one of the co-investigators will discuss the studies with all eligible patients. Interested patients will be provided with a copy of the consent form(s), and the study coordinator or PI (or a co-investigator) will carefully go over the consent with each candidate before he/ she signs. We will strive to ensure that all patients understand the nature of the study and all their questions will be answered. The original consent form will be placed in the study files, in a secure, locked cabinet. Potential subjects will be contacted during regularly scheduled clinic visits, but may be contacted at home by study personnel if they are known to meet the eligibility criteria. The PI and study nurse involved in the study are regular staff of the program. Samples obtained from patients specifically for these studies will be collected as approved by the IRB. This is anticipated to occur during specified study visits.

4. Potential Risks: The study entails physical risk associated with venipuncture to obtain blood samples; administration of rivaroxaban; and pneumatic occlusion cuff placed around the arm to a suprasystolic pressure (~ 200 mmHg) during the assessment of microvascular blood flow. The most significant risks of blood tests are discomfort and bruising. There is still limited clinical experience with the use of rivaroxaban in the general population, and even less so in SCD. However, published studies indicate that the most common complications of rivaroxaban are bleeding, bruising, peripheral edema, dizziness, headache, pyrexia, fatigue, syncope, pruritus, rash, blister, diarrhea, thrombocytopenia, extremity pain, and back pain. Pneumatic occlusion of the arm to a suprasystolic pressure is uncomfortable. However, this technique has been safely performed in SCD patients. Patients will be monitored very closely for any laboratory or clinical complications during the course of the studies.

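### Table 2 schedules no hemoglobin on study drug, although a 2 g/dL fall is a limb of major bleeding and of the drug-stopping rule

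*Combined protocol and SAP*

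**What the plan says.** Under Safety Assessment, major bleeding has three limbs: bleeding into a critical site, a "decrease in hemoglobin concentration of at least 2g/dL from baseline", and prolonged bleeding that needs transfusion. Termination Criteria repeats this definition and stops study drug when it is met.

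The plan refers to blood counts and laboratory monitoring in several places:

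- The synopsis (Clinical and Laboratory Evaluations) says that in the Treatment Phase "we will also obtain a complete blood count, routine chemistries to assess liver and renal function", together with a pregnancy test. It names no visit. The same sentence then separately describes repeat laboratory studies before the second period, which serve as that period's baseline.
- Research Design and Methods says "Table 2 provides a detailed schedule of assessments for the study period". The Hematology row of Table 2 is defined in footnote 2 as "CBC with differential and reticulocyte count". It is marked at screening, the two baselines and follow-up only.
- The Treatment paragraph says "PT/INR will be monitored by an unblinded investigator to assess compliance", but the Coags row has the same blanks as the Hematology row.
- Potential Risks promises that "Patients will be monitored very closely for any laboratory or clinical complications during the course of the studies". Safety Assessment mentions routine laboratory tests. Neither names a CBC or a visit.
- The Data and Safety Monitoring Plan says "all of the available safety data will be presented by treatment group to the DSMB in a confidential report".

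Exclusion criterion c removes patients with "baseline Hb < 5.5 g/dL", so a patient may enter at 5.5 g/dL.

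**The concern.** A rule that stops treatment on a laboratory value needs that value while the patient is being treated. The other two limbs of major bleeding show themselves clinically. The hemoglobin limb can be met without symptoms, so it depends most on a scheduled test. If staff follow Table 2, they take hemoglobin before each period's dosing and again only after drug has been stopped. A silent fall would then be missed, or found when the rule can no longer act in that period.

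Safety is Specific Aim C, and Potential Risks acknowledges that experience with rivaroxaban in sickle cell disease is very limited. The low entry floor for hemoglobin leaves little margin for late detection.

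**Working it through.** The plan gives no figure to reproduce here. The check is a reading of Table 2 followed by day counts.

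**Table 2, by visit.** The rows checked have the same number of columns as the visit header. The Biomarkers and laser Doppler rows match the timing given under Assessments, so the column alignment can be relied on.

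| Row | Screen | BL 1 | Wk 2 | Wk 4 | BL 2 | Wk 2 | Wk 4 | F/U |
|---|---|---|---|---|---|---|---|---|
| Hematology (CBC) | X | X | – | – | X | – | – | X |
| Coags | X | X | – | – | X | – | – | X |
| Biomarkers | – | X | X | X | X | X | X | – |
| Laser Doppler | – | X | – | X | X | – | X | – |
| Pregnancy test | – | X | X | X | X | X | X | – |
| Adverse event probe | – | X | X | X | X | X | X | X |

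Of the four on-treatment visits, CBC is marked at 0 and coagulation tests at 0. Biomarkers, pregnancy test and adverse event probe are each marked at 4.

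**Two readings of the synopsis.**

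1. The Treatment Phase CBC means the on-treatment visits. Table 2 then omits it.
2. It means the baseline draws. This is possible because Research Design and Methods counts the phase as 10 weeks with washout included, so the second baseline lies inside it. The texts then agree, but no hemoglobin is scheduled on drug.

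The synopsis lists CBC, chemistries and pregnancy test together, yet of these Table 2 marks only the pregnancy test at Weeks 2 and 4.

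**Gaps if Table 2 governs.** Inputs are 28 days of dosing per period and a washout of 14 ± 3 days. Follow-up is at week 12 of a schedule whose treatment ends at week 10 (Research Design and Methods), at Wk 6 against Wk 4 (Table 2), or four weeks after the last dose (synopsis).

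- Last Period 1 dose to next hemoglobin: 14 − 3 = 11 to 14 + 3 = 17 days.
- Period 1 baseline to next hemoglobin: 28 + 11 = 39 to 28 + 17 = 45 days.
- Last Period 2 dose to follow-up hemoglobin: 12 − 10 = 2 weeks, or 6 − 4 = 2 weeks, so 14 days; by the synopsis, 28 days.
- Period 2 baseline to follow-up hemoglobin: 28 + 14 = 42 or 28 + 28 = 56 days.

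The plan gives a half-life of 6 to 7 hours, and up to 13 hours in elderly patients. Even 11 days is then 264 / 13 ≈ 20 half-lives, so these samples are taken off drug.

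**Margin at the entry floor.** 5.5 − 2.0 = 3.5 g/dL; 2.0 / 5.5 = 36%.

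**With CBCs at Weeks 2 and 4.** The longest gap during treatment is 14 days. Extra assays: 34 × 4 = 136, or 32 × 4 = 128 if 32 patients are enrolled, as the synopsis and Human Subjects state.

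**The case against.** The strongest reply is that the synopsis already provides the test. It lists the pre-Period 2 laboratory work separately, so the Treatment Phase CBC is more naturally an additional, on-treatment one. Table 2 also looks incomplete: PT/INR is to be monitored for compliance, yet no on-treatment coagulation test is marked. On this view the table lost some ticks and nobody chose to omit the test. That is probably right about intent. It does not remove the problem, because no visit is named and the table is what the plan calls its detailed schedule.

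Other points have some force:

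- Adverse event probes and vital signs are marked at all four on-treatment visits, and a clinical bleed could prompt an unscheduled CBC. A large fall from a low starting value may well cause symptoms. This narrows the risk to silent falls.
- The hemoglobin limb sits under the heading of bleeding, so an isolated fall might not count. Appendix 2, cited in the Treatment paragraph, is not in the text available to us and may settle this.
- A Week 4 CBC comes at the end of dosing and cannot stop drug in that period. Only the Week 2 draws (34 × 2 = 68 of 136) serve the stopping rule; the Week 4 draws serve ascertainment.
- More testing will find more falls. If these are judged treatment-related major bleeds, they also count toward the rule that ends the study at three participants.
- The primary endpoints are soluble VCAM-1 and IL-6, and a missing CBC does not affect how they are measured.

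These points limit the harm and add to the cost of the fix. None supplies a scheduled on-drug hemoglobin.

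**Conclusion.** The concern holds. Table 2 marks a CBC at 0 of 4 on-treatment visits, and no other text assigns one to a visit. If Table 2 governs, the next hemoglobin after each period's baseline comes 39 to 45 days later (Period 1) and 42 or 56 days later (Period 2), after dosing has ended. Scheduled data then cannot trigger the hemoglobin limb during treatment. If the synopsis governs, the table is wrong. The correction is the same in both cases.

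The conclusion assumes that staff work from Table 2 and that each baseline sample precedes that period's first dose. It does not claim that hemoglobin could never be measured on drug, or that a fall would have recovered by the next CBC; no recovery rate is given. The frequency of such falls is not estimated, because the documents give no within-patient hemoglobin SD. This should be corrected for safety ascertainment, but it is not a flaw in the primary efficacy analysis.

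**What to change.** Mark a CBC in Table 2 at Weeks 2 and 4 of both periods, taken at the biomarker draw, and name those visits in the synopsis sentence. Judge each fall against that period's own baseline, consistent with the plan's use of the repeat laboratory studies as the Period 2 baseline. The drug-stopping rule may stay.

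Two secondary changes would help:

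- In the final safety report, show falls of at least 2 g/dL with a recorded bleed separately from isolated falls, by treatment and period. Use patients with a post-dose hemoglobin as the denominator. The board already receives safety data by treatment group, but this table is not specified.
- State one follow-up time, either 2 or 4 weeks after the last dose.

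The cost is at most 136 CBC assays (128 with 32 patients) and a line in a safety table, with no new visit or venipuncture. The drawback is that more isolated falls will be found on either treatment, and some will stop study drug or count toward study termination. Patients who leave early are not replaced. The sample size allows 34 − 30 = 4 losses, or 32 − 30 = 2 if only 32 are enrolled.
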